6.12.13 Incidence of variceal haemorrhage, ascites or hepatic encephalopathy over 28 days

The number and percentage of patients who experience a variceal haemorrhage between Baseline and Day 28 will be summarised by treatment group. The associated 95% Clopper-Pearson exact confidence intervals will also be presented.

The number and percentage of patients who have ascites between baseline and day 28 will be summarised by treatment group. The associated 95% Clopper-Pearson exact confidence intervals will also be presented.

Patients who have a hepatic encephalopathy score of 2 or 3 in the data collected for the Child-Pugh score will be classed as having hepatic encephalopathy (Yes). Any patient with a score of 1 will be classed as not having hepatic encephalopathy (No). the number and percentages of patients who have hepatic encephalopathy between baseline and day 28 will be summarised by treatment group. The associated 95% Clopper-Pearson exact confidence intervals will also be presented.

All variceal haemorrhage and ascites data will be listed. Hepatic encephalopathy will be included into the Child-Pugh listing.

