### 7.3 Exclusion Criteria

1. Pregnant or lactating females.
2. Spontaneous liver function improvement defined by decrease of bilirubin level and MDF of >10% within 5 days of hospital admission
3. Grade 4 hepatic encephalopathy (West Haven Criteria)
4. Type 1 hepatorenal syndrome (HRS) or a serum creatinine >2 x ULN or the requirement for haemodialysis
5. History of hypersensitivity to any substance in DS102 capsules or placebo capsules.
6. Alcohol abstinence of >6 weeks prior to screening
7. Duration of clinically apparent jaundice >3 months prior to baseline
8. Other causes of liver disease including:
  - a. Evidence of chronic viral hepatitis (Hepatitis B DNA positive or HCV RNA positive)
  - b. Biliary obstruction
  - c. Hepatocellular carcinoma
  - d. Wilsons disease
  - e. Budd Chiari Syndrome
  - f. Non-alcoholic fatty liver disease
9. History of or active non-liver malignancies other than curatively treated skin cancer (basal cell or squamous cell carcinomas).
10. Previous entry into the study
11. AST >400 U/L or ALT >270 U/L
12. Treatment with any experimental drug within 30 days prior to Day 0 visit (Baseline), or 5 half-lives (whichever is longer).
13. Patients who have used dietary supplements rich in omega-3 oromega-6 fatty acids in the four weeks prior to baseline.
14. Patients dependent on inotropic support (adrenaline or noradrenaline), including Terlipressin
15. Active variceal haemorrhage on this admission requiring more than 2 units of blood to maintain haemoglobin level within 48 hours
16. Presence of refractory ascites
17. Untreated or unresolved sepsis
18. Patients with cerebral haemorrhage, extensive retinal haemorrhage, acute myocardial infarction (within last 6 weeks) or severe cardiac arrhythmias (not including atrial fibrillation)
19. Known infection with HIV at screening.
20. Significant systemic or major illnesses other than liver disease that, in the opinion of the investigator, would preclude or interfere with treatment with DS102 and/or adequate follow up.
21. Previous liver transplantation

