#### Biomarker (as detailed in Section 9.2.8.3)

In addition, the following assessments of nutritional status will also be performed, with nutritional interventions provided where required:

- BMI
- Bedside Subjective Global Assessment (SGA) score (0, 1, 2, and 3). Patients will be classified into the following categories:
  - Well nourished (0)
  - Mild malnutrition (1)
  - Moderate malnutrition (2)
  - Severe malnutrition (3)

If all study entry criteria are satisfied the Investigator will randomise the patient and provide the patient with the designated IMP or placebo from one of the patient treatment packs available at the site.

The first dose of IMP or placebo will be administered at site once all baseline assessments have been completed. The patient will take their second dose of IMP or placebo in the evening of Day 0. The capsules will then be administered twice-daily.

#### 8.2.4 Visit 3/Day 3

The following assessments will be performed:

- Physical examination (as detailed in Section 9.2.2)
- Vital signs (blood pressure, heart rate and body temperature), as detailed in Section 9.2.4)

- Pharmacokinetic sampling (as detailed in Section 9.2.8.1)
- Samples for clinical laboratory safety tests (haematology, serum biochemistry, and coagulation tests as detailed in Section 9.2.5)
- MELD (as detailed in Section 9.1.1)
- MDF (as detailed in Section 9.1.7)
- m-SOFA (as detailed in Section 9.1.8)
- APACHE II score (as detailed in Section 9.1.9)
- Total bilirubin (as detailed in Section 9.1.2)
- CK-18 (as detailed in Section 9.1.6)
- AST:ALT (as detailed in Section 9.1.3)
- Child pugh score (as detailed in Section 9.1.5)
- Gamma GT (as detailed in Section 9.1.4)
- Collection of acute kidney injury, ascites and variceal haemorrhage data
- AE assessment (as detailed in Section 11)
- Concomitant medication assessment (as detailed in Section 9.2.10)
- Biomarker (as detailed in Section 9.2.8.3)
- Lille Score (as detailed in Section 9.1.10)
- West Haven criteria assessment (as detailed in Section 9.1.11)

### 8.2.5 Visit 4/Day 5

The following assessments will be performed:

- Physical examination (as detailed in Section 9.2.2)
- Vital signs (blood pressure, heart rate and body temperature), as detailed in Section 9.2.4)
- Pharmacokinetic sampling (as detailed in Section 9.2.8.1)
- Samples for clinical laboratory safety tests (haematology, serum biochemistry, and coagulation tests as detailed in Section 9.2.5)
- MELD (as detailed in Section 9.1.1)

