**Table 1: Child-Pugh Score (Jackson & Gleeson 2010)**

Factor	1 point	2 points	3 points
Bilirubin ( $\mu\text{mol litre}^{-1}$ )	< 34	34–50	< 50
Albumin (g litre $^{-1}$ )	> 35	28 – 35	< 28
INR	< 1.7	1.7 – 2.2	> 2.2
Ascites	None	Controlled	Refractory
Hepatic encephalopathy	None	I – II or controlled	III – IV or refractory

Blood samples will be taken to assess the Child-Pugh score at Visit 2/Baseline, Visit 3/Day 3, Visit 4/Day 5, Visit 5/Day 7, Visit 6/Day 14, Visit 7/Day 21, Visit 8/Day 28/Early Termination and Visit 9/Day 90/Follow up.

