### 13.2 Informed Consent and Inclusion of Subjects Incapable of Providing Informed Consent

It is the responsibility of the Investigator, or a person designated by the Investigator (if acceptable to local regulation), to obtain written informed consent from each individual participating in this study after adequate explanation of the aims, methods, objectives and potential hazards of the study. If the patient is incapacitated, e.g. in the case of Grade II or Grade III hepatic encephalopathy, a relative (with the exception of certain countries) or legal representative will be responsible for giving informed consent on behalf of the patient in accordance with the Declaration of Helsinki.

Additional requirements for representatives giving informed consent for an incapacitated patient may apply in certain countries. Investigators in these countries will be notified accordingly in a protocol clarification memo and the patient information sheet and informed consent will be adapted.

Clinical trials are essential to improve the outcomes of subjects with critical illness, such as the target population of this study. However, individuals with Severe Acute Alcoholic Hepatitis comprise a critically ill patient population in which it may be difficult to obtain robust informed consent. The value and generalisability of study results is contingent upon recruitment of a representative sample of patients, ensuring that consenting participants and non-consenting participants are not systematically different. As a result, it may be necessary that persons who are incapable of giving informed consent are included in this study.

Robust measures are in place to ensure that in such situations informed consent is obtained

from an appropriate relative or legal representative. A separate ICF will be used in such cases. When a potential research subject who is deemed incapable of giving informed consent is able to give assent to decisions about participation in research, the recruiting physician must seek that assent in addition to the consent of the legally authorised representative. The potential subject's dissent must be respected.

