6.3 General Derivations

- Definition of baseline

Baseline is defined as the last non-missing value (including scheduled and unscheduled assessments) prior to the patient receiving study treatment.

- Incomplete dates

For calculation purposes, incomplete dates will be completed using worst case. Further details are detailed in the relevant sections as required.

- Non-numeric values recorded in a numeric field

In the case where a variable is recorded as “>x”, “ $\geq x$ ”, “ $<x$ ” or “ $\leq x$ ” in a numeric field, then for analysis purposes a value of x will be taken. Where a range of values is quoted the midpoint of the range will be taken. For example, if a laboratory safety parameter is reported as being below the limit of quantification or $< x$, the value of the limit will be used in the calculation of summary statistics. The recorded value will be reported in listings.

- Methods for handling withdrawals and missing data

Imputation of any data will be detailed in the relevant sections.

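### SAP 6.12.13 is titled an incidence over 28 days but counts presence, so encephalopathy already there at entry (and ascites, unless the eCRF records only new events) is reported as incident

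*SAP*

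**What the plan says.** Protocol 5.2 and SAP 2.2 list, as a secondary endpoint, the incidence over 28 days of three complications of liver disease. Neither defines a case. SAP 6.12.13 supplies the counting rules:

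- Ascites: "The number and percentage of patients who have ascites between baseline and day 28 will be summarised by treatment group".
- Hepatic encephalopathy: "Patients who have a hepatic encephalopathy score of 2 or 3 in the data collected for the Child-Pugh score will be classed as having" the condition, and patients who have it in the same window are counted by arm.
- Variceal haemorrhage is worded as an event that a patient experiences, so it is not part of this point.

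Each percentage gets an exact 95% interval per arm; no between-arm test is planned in that section. Secondary endpoints use the full analysis set (SAP 6.5), and percentages are by default based on non-missing observations (SAP 6.1).

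On where the window starts, SAP 6.3 says: "Baseline is defined as the last non-missing value (including scheduled and unscheduled assessments) prior to the patient receiving study treatment". Protocol 8.2.3 agrees: "The first dose of IMP or placebo will be administered at site once all baseline assessments have been completed".

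On who may enter, Protocol 7.3 excludes "Presence of refractory ascites" and "Grade 4 hepatic encephalopathy (West Haven Criteria"), and no lesser degree of either condition. Protocol 13.2 plans for consent by a representative "in the case of Grade II or Grade III hepatic encephalopathy".

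**The concern.** An incidence is the share of patients free of a condition who then develop it. The rules for ascites and encephalopathy ask only whether the patient has the condition at some time from baseline to Day 28. A patient who enters with controlled ascites or Grade II encephalopathy can therefore be a case without anything new having happened. Patients with severe acute decompensated disease may well have either condition at entry, and the eligibility criteria allow it.

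The risk is one of interpretation. A percentage with an exact interval under a title that says incidence is likely to be read as complications arising on treatment. Baseline cases raise that percentage in both arms and hide part of any difference in new cases.

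**Working it through.** **Plan figure to reproduce.** There is none for this endpoint. The documents give no baseline prevalence, onset rate or expected percentage for either condition. The one design figure used below is 60 randomised patients per arm (SAP 3).

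**Step 1: can baseline cases be counted?**

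- Encephalopathy: in the Child-Pugh table (Protocol 9.1.5) a score of 2 covers "I – II or controlled", so even Grade I at entry meets the case definition. Only Grade 4 is excluded.
- Ascites: only the refractory form is excluded, so other ascites at entry meets the wording.
- Visit 2: baseline is pre-dose, and the SAP does not say whether it lies inside the window. Leaving it out does not cure the problem. Appendix 2 of the protocol schedules the Child-Pugh score and the ascites data at Days 3, 5, 7, 14, 21 and 28, and a baseline case still present at any one of those visits is counted.

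**Step 2: what the count estimates.** Let p be baseline prevalence, q the share of baseline cases that are counted, and r the onset risk among patients free of the condition at baseline.

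Counted proportion = p·q + (1 − p)·r

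If Visit 2 counts, q = 1. If it does not, q is the share of baseline cases seen with the condition at any of the six later visits. With q equal in the two arms, or close to 1 in both, the first term cancels or nearly cancels:

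Counted difference ≈ (1 − p)·(r placebo − r DS102)

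**Step 3: illustration.** All rates are assumptions: onset 30% on placebo and 15% on DS102 (a 15-point difference), and q = 1.

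| Assumed p | Placebo counted | DS102 counted | Difference |
|---|---|---|---|
| 30% | 0.30 + 0.70 × 0.30 = 51.0% | 0.30 + 0.70 × 0.15 = 40.5% | 10.5 points |
| 50% | 0.50 + 0.50 × 0.30 = 65.0% | 0.50 + 0.50 × 0.15 = 57.5% | 7.5 points |
| 70% | 0.70 + 0.30 × 0.30 = 79.0% | 0.70 + 0.30 × 0.15 = 74.5% | 4.5 points |

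**Step 4: one arm in counts (assumed).** Of 60 patients, 36 have the condition at baseline and 6 of the other 24 develop it. The SAP rule gives (36 + 6)/60 = 70.0% (exact 95% interval 56.8% to 81.2%). Incidence among those at risk is 6/24 = 25.0% (9.8% to 46.7%).

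**The case against.** The best reply has four parts.

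*The comparison is fair.* Baseline status is fixed before randomisation, so baseline cases are balanced on average and presence during the period is a legitimate between-arm contrast. This stands: the figure is mislabelled and diluted, not biased as a measure of presence.

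*Other outputs cover the ground.* Ascites data are listed in full, and encephalopathy appears in the Child-Pugh listing (SAP 6.12.13). West Haven grade is modelled with baseline as covariate and summarised by visit (SAP 6.12.11). Child-Pugh is analysed as change from baseline (SAP 6.13.4), and treatment-emergent events are tabulated by preferred term (SAP 6.16.1). These are real mitigations, but none changes the 6.12.13 percentage. Adverse-event percentages are also based on everyone in the analysis set (SAP 6.1). With complete reporting of new cases they would show (1 − p)·r, which is 21.0% versus 10.5%, 15.0% versus 7.5% or 9.0% versus 4.5% in the illustration.

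*The ascites page may record only new events.* Ascites is collected in one schedule item with acute kidney injury and variceal haemorrhage, both event-type outcomes, and the eCRF is not in the documents. If so, the ascites part is only a wording error. The encephalopathy part rests on a status score either way.

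*The table shells may clarify.* They are a separate document (SAP 1) and could carry a baseline row or footnote.

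A reader might also infer something stronger: that different persistence in the two arms could make the summary point the wrong way. The documents do not support that. In the illustration, reversal needs q on DS102 to exceed q on placebo by more than 15 × p/(1 − p) inverted, that is 15 × (1 − p)/p = 35, 15 or 6.4 points at p = 30%, 50% or 70%. As q cannot exceed 1, this is impossible once placebo q is above 65%, 85% or 93.6%. A q much below 1 would require many baseline cases to clear before Day 3 and not be recorded again at any visit to Day 28, and nothing in the documents suggests this.

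**Conclusion.** The title and the counting rule disagree. As written, SAP 6.12.13 reports presence at some time from baseline to Day 28, among all patients with data, and calls it incidence. This is clear for encephalopathy. For ascites it holds unless the eCRF captures only new events.

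The supported effect is dilution: a difference in new cases shrinks by about (1 − baseline prevalence) when nearly all baseline cases are counted. The 10.5, 7.5 and 4.5 points rest wholly on assumed onset and prevalence, so the true size is unknown.

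Severity is minor. SAP 6.14 treats secondary endpoints as descriptive, and the primary MELD analysis is untouched. Confidence is medium, because the eCRF page and the table shells could not be seen.

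**What to change.** Amend SAP 6.12.13 before unblinding; SAP 6.2 already provides for an amendment after the blinded data review.

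- For ascites and for encephalopathy, define an incident case as first presence after the first dose and up to Day 28 in a patient without the condition at baseline (Visit 2). Use those patients as the denominator.
- Report by arm the number with the condition at baseline, and the number who died by Day 28 without onset, since death ends the time at risk.
- Keep the present count beside it, relabelled as presence at any time from baseline to Day 28, and state whether Visit 2 counts.
- Check the eCRF ascites page. If it takes only new events, correct the ascites wording to say so.

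The cost is SAP text and programming. Protocol 8.2.3 already collects ascites data and the Child-Pugh score at Visit 2. The downside is precision: the at-risk group is 60 × (1 − p), about 42, 30 or 18 per arm at assumed prevalence of 30%, 50% or 70%. The exact 95% interval around roughly 30% widens from 18.8–43.2% (18/60) to 17.6–47.1% (13/42), 14.7–49.4% (9/30) or 9.7–53.5% (5/18). That is a reason to show both summaries rather than onset alone.

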### 5.2 Secondary Endpoints

- Change in total bilirubin from baseline to Day 7, 14, 21 and 28
- Proportion of patients showing a 25% reduction of bilirubin at day 7, 14, 21, and 28.
- Change in serum Cytokeratin18-M30/M65 from baseline to Day 7, 14, 21 and 28
- Change in AST levels from Baseline to Day 7, 14, 21 and 28
- Change in AST:ALT ratio from Baseline to Day 7, 14, 21, 28
- Change in MDF score from baseline to Day 7, 14, 21 and 28.
- Proportion of patients showing a 25% reduction in MELD score from baseline to Day 7, 14 and 21
- Change in m-SOFA from baseline to Day 7, 14, 21 and 28
- Proportion of patients with a 2-point worsening of m-SOFA from baseline at Day 7, 14, 21 and 28
- Change in hepatic encephalopathy as assessed by West Haven criteria, from baseline at Day 7, 14, 21 and 28 from baseline to Day 28
- Incidence of acute kidney injury over 28 days (defined by requiring medicinal or mechanical support)
- Incidence of variceal haemorrhage, ascites or hepatic encephalopathy over 28 days

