#### 9.1.11 West Haven Criteria

The West Haven Criteria is used to classify the severity of hepatic encephalopathy with a grading of 1 – 4, Grade 1 being the least serious with the patient having a trivial lack of awareness to Grade 4 in which the patient is in a state of unconsciousness.

Grade	Criteria
1	Trivial lack of awareness Euphoria or anxiety Shortened attention span Impaired performance of addition
2	Lethargy or apathy Minimal disorientation of time or place Subtle personality changes Inappropriate behaviour
3	Somnolence to semi-stupor but responsive to verbal stimuli Confusion
4	Gross disorientation Coma (unresponsive to verbal or noxious stimuli)

(Ferenci et al. 1998)

West Haven criteria will be assessed at Visit 1/Screening , Visit 2/Baseline, Visit 3/Day 3, Visit 4/Day 5, Visit 5/Day 7, Visit 6/Day 14, Visit 7/Day 21, Visit 8/Day 28/Early Termination and Visit 9/Day 90/Follow up.

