### 11.1.4 Reporting of AEs and SAEs

All AEs must be recorded in the eCRF, defining relationship to IMP and severity.

**As soon as the Investigator is aware of a potential SAE, he/she should contact the pharmacovigilance (PV) contract research organisation (CRO) monitor by phone, fax or e-mail, and, in any case, no later than 24 hours after the knowledge of such a case. The contact information is provided in the ISF.**

At the time of the call, the Investigator must provide, as a minimum requirement, the patient number, birth date, nature of the SAE and a preliminary assessment of causality. The Investigator should follow-up the initial notification of the potential SAE by faxing a copy of the SAE reporting form to the PV CRO at the number provided in the ISF. The faxed SAE reporting form should be sent to the PV CRO within 24 hours of knowledge of such a case.

Follow-up information on an existing SAE that is fatal or life-threatening should be reported by the Investigator to the PV CRO within five days after the initial report. Where appropriate, hospitalisation or autopsy reports should be made available. All SAEs will be followed up until resolution (i.e., asymptomatic, stabilization or death).

AEs should be reported from the first dose of study drug up to and including the follow up period. Following completion of the study, if the Investigator becomes aware of any AE that is potentially related to the IMP the Sponsor should be notified.

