## 15. 2 Appendix 2: Study Flowchart – Double-Blind Phase

Visit	Screening/ Visit 1	Baseline/ Visit 2	Day 3/ Visit 3	Day 5/ Visit 4	Day 7/ Visit 5	Day 14/ Visit 6	Day 21/ Visit 7	Day 28/Visit 8/ Early Termination	Day 90/Visit 9/ Follow Up
Day		0	3	5	7	14	21	28	90
Visit Window	N/A	±0 day	±0 day	±0 day	±2 day	±2 day	±2 day	±1 day	±10 days
Informed Consent 	X								
Inclusion/Exclusion	X	X							
Demographics	X								
Patient Randomisation		X							
Medical History	X	X							
Physical Examination	X	X	X	X	X	X	X	X	X
Vital Signs	X	X	X	X	X	X	X	X	X
ECG (6-lead or 12-lead)	X	X							X
Pharmacokinetic Sampling 		X	X	X	X	X	X	X	
Exploratory Blood Sample		X				X		X	
Clinical Laboratory Tests 	X	X	X	X	X	X	X	X	X
Virology	X								
Urinalysis	x								
Liver ultrasound	X								
Pregnancy Test 	X	X				X		X	
MELD	X	X	X	X	X	X	X	X	X
MDF	X	X	X	X	X	X	X	X	X
m-SOFA		X	X	X	X	X	X	X	X
West Haven Criteria	X	X	X	X	X	X	X	X	X
APACHE II		X	X	X	X	X	X	X	X
Lille score		X	X	X	X	X	X	X	X
Total Bilirubin	X	X	X	X	X	X	X	X	X
CK-18		X	X	X	X	X	X	X	X
ALT, AST	X	X	X	X	X	X	X	X	X
Child Pugh Score		X	X	X	X	X	X	X	X
Gamma GT		X	X	X	X	X	X	X	X
Assessment of nutritional status		X				X		X	
Collection of acute kidney injury, ascites and variceal haemorrhage data		X	X	X	X	X	X	X	
Biomarker		x	x	x	x	x	x	x	

Visit	Screening/ Visit 1	Baseline/ Visit 2	Day 3/ Visit 3	Day 5/ Visit 4	Day 7/ Visit 5	Day 14/ Visit 6	Day 21/ Visit 7	Day 28/Visit 8/ Early Termination	Day 90/Visit 9/ Follow Up
Mortality			X	X	X	X	X	X	X
IMP/Placebo Administration		X -----X							
AE Assessment		X	X	X	X	X	X	X	
Concomitant Medication Assessment	X	X	X	X	X	X	X	X	

 Includes biochemistry, haematology, and coagulation tests. Caeruloplasmin will be collected at screening only

 Female Patients of child bearing potential only.

 Patient may be required to reconsent after Visit 1 if new information is made available.

 Trough plasma PK samples will also be obtained prior to the first daily dose on the indicated days.

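### 28-day incidence of hepatic encephalopathy is read only from the Child-Pugh item on visit days, so an episode that resolves or proves fatal before the next visit can be counted as No

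*SAP*

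**What the plan says.** - **Endpoint.** Protocol 5.2 lists as a secondary endpoint "Incidence of variceal haemorrhage, ascites or hepatic encephalopathy over 28 days".
- **Rule.** SAP 6.12.13 reports the three complications one by one, as counts and percentages per arm with Clopper-Pearson intervals. For encephalopathy, Yes goes to "Patients who have a hepatic encephalopathy score of 2 or 3 in the data collected for the Child-Pugh score", and a score of 1 gives No. No AE, West Haven or event-form source is named, and the data appear only in the Child-Pugh listing.
- **Timing.** Protocol 9.1.5 takes blood samples to "assess the Child-Pugh score at Visit 2/Baseline, Visit 3/Day 3, Visit 4/Day 5, Visit 5/Day 7, Visit 6/Day 14", then at Days 21, 28 (or early termination) and 90. In its table, two points are given for encephalopathy that is "I – II or controlled".
- **Event row.** The double-blind flow chart (Protocol, Appendix 2) has a row headed "Collection of acute kidney injury, ascites and variceal haemorrhage data", marked at every visit from baseline to Day 28. The pilot flow chart and the visit lists in 8.2.3 to 8.2.9 carry the same item. None of them mentions encephalopathy.
- **Other sources.** Under Protocol 9.1.11, "West Haven criteria will be assessed at Visit 1/Screening , Visit 2/Baseline, Visit 3/Day 3, Visit 4/Day 5, Visit 5/Day 7", and from there on the same later visits as Child-Pugh. Under Protocol 11.1.4, "AEs should be reported from the first dose of study drug up to and including the follow up period". SAP 6.16.1 lists AEs with times of onset and cessation.

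**The concern.** The endpoint is an incidence over a period, but the rule records a patient's state on up to seven days. After Day 7 those days are a week apart. An episode scored as none at the next visit, or followed by death before it, leaves no trace in this table, although dated AE data that could show it are collected anyway.

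The error runs one way: the rule can miss cases arising between visits but does not create any. Fatal episodes are among those it can miss, and these are the outcomes a reader of this endpoint would most want counted. The rule also starts at baseline without separating prevalent from new cases. Protocol 7.3 excludes only Grade 4 encephalopathy, and Protocol 13.2 foresees consent by a representative for patients in Grade II or III. Encephalopathy present at Day 0 therefore counts as Yes alongside new onset.

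**Working it through.** **The plan's own figures.** The documents give no rate, power or detection figure for encephalopathy. Their one sample-size figure (55 per group, power 0.8014) concerns MELD change and does not bear on this point.

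**What the rule does**
1. Child-Pugh is scheduled for everyone at baseline. SAP 6.1 bases percentages on non-missing observations, so a patient who dies before a later visit normally stays in the denominator on the scores already recorded.
2. If those scores are all 1, the patient is No.
3. SAP 6.12.13 does not say how visits combine. A patient scoring 1 at one visit and 2 at another fits both of its sentences. I take any score of 2 or 3 as Yes.
4. West Haven is done on the same days and so adds no information between visits.

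**Share of episodes touching no visit day**

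Inputs: post-baseline visit days 3, 5, 7, 14, 21 and 28, on schedule. Assumptions: onset equally likely on each of Days 1-28, and an episode of length *d* occupies *d* consecutive days. The documents give no durations, so *d* is varied.

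The runs of days without a visit are 1-2, 4, 6, 8-13, 15-20 and 22-27, with lengths 2, 1, 1, 6, 6 and 6. A run of length *L* holds max(0, *L* - *d* + 1) onsets whose episode fits wholly inside it. Divide by 28 onsets, or by 21 for onset on Day 8 or later. Episodes running past Day 28 include Day 28 and count as detected.

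| *d* (days) | Missed onsets, Days 1-28 | Share | Missed onsets, Day 8 or later | Share |
|---|---|---|---|---|
| 2 | 1 + 5 + 5 + 5 = 16 | 16/28 = 57% | 15 | 15/21 = 71% |
| 3 | 4 + 4 + 4 = 12 | 12/28 = 43% | 12 | 12/21 = 57% |
| 4 | 3 + 3 + 3 = 9 | 9/28 = 32% | 9 | 9/21 = 43% |
| 5 | 2 + 2 + 2 = 6 | 6/28 = 21% | 6 | 6/21 = 29% |

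A continuous-time version, summing max(0, gap - *d*) over the gaps 3, 2, 2, 7, 7 and 7 and dividing by 28, gives the same shares. At 7 days it gives zero.

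The figures hold for visits on schedule. The windows of 2 days either side at Days 14 and 21 allow a gap of 23 - 12 = 11 days.

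**Fatal episodes (illustration only)**

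The Protocol (1.1) cites mortality exceeding 30% without a time horizon in that sentence. Assume 28-day mortality of 10% to 30%, and that 25% to 50% of deaths follow an episode that began after the last visit. In an arm of 60 that is 60 × 0.10 × 0.25 = 1.5 to 60 × 0.30 × 0.50 = 9 patients. They would be No only if all their earlier scores were 1. Neither range comes from the documents.

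**The case against.** The other side has substance, and much of it stands.

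- **Controlled encephalopathy scores 2.** An episode between visits that is still under treatment can be Yes at the next visit. The loss is certain only for episodes scored as none at that visit or fatal before it. This stands, and it makes every percentage above an upper bound.
- **Episodes are not patients.** A patient with any positive visit is already Yes, so recurrent, longer or baseline encephalopathy is caught. A reader might take 57% or 71% as the share of patients misclassified. The documents do not allow that share to be estimated.
- **Patients who leave.** A reader might infer that early leavers are lost as well. Protocol 7.5 and 8.1 call for an early-termination visit, and 8.2.9 includes Child-Pugh in it. Those who leave alive should be assessed, apart from any who do not attend.
- **Contrast with the other complications.** The row for kidney injury, ascites and haemorrhage is also completed at visits. The documents do not say whether that form asks about the interval since the last visit. Its omission of encephalopathy is a fact; a superior method for the other events is not established.
- **Consequence.** There is no between-arm test in SAP 6.12.13, and SAP 6.14 treats secondary endpoints as descriptive. West Haven grade has its own model in SAP 6.12.11, and missed episodes may appear in the AE tables.

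What remains is that the stated rule can undercount a period incidence when a better source is already in the database.

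**Conclusion.** The point holds as a limited defect in one descriptive secondary endpoint. The rule in SAP 6.12.13 can classify as No a patient who had encephalopathy within 28 days, mainly through deaths before the next visit and episodes that resolved between visits. The table above bounds the share of episodes touching no visit, given on-schedule visits, even onset and the assumed durations. The share of patients affected is unknown.

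A reader might go further and infer a biased treatment comparison. Unequal undercounting would require DS102 to change the duration or lethality of episodes, and the documents give no figure for that. Nor is encephalopathy uncollected in this trial, and no alpha or decision depends on the table. The change is worth making because the undercount is built into the rule and the remedy is cheap.

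**What to change.** **SAP 6.12.13**
- Count a patient as Yes if either holds: the Child-Pugh encephalopathy item is 2 or 3 at any assessment up to Day 28 or early termination; or an AE or SAE coded to a fixed MedDRA list of hepatic encephalopathy terms has onset from first dose to Day 28.
- Show patients with encephalopathy already present at baseline separately from those with post-baseline onset.
- Show the visit-only count alongside the combined count.

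West Haven need not be added as a between-visit source, since it falls on the same days.

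**Protocol 8.2.3 to 8.2.9 and Appendices 1 and 2**
- Add hepatic encephalopathy to the existing event-collection row.

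**Cost.** A few sentences and a term list in the SAP, and one addition to an existing row in the visit lists, flow charts and eCRF. AE data are already collected, so the SAP change can stand alone. The downside is that AE-based cases depend on investigator reporting. That reporting is blinded (Protocol 12.4), and the visit-only count shows how much the result rests on it.
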